6.3 Exploratory objectives

6.3.1 Variables

Commercially Confidential Information

Commercially Confidential Information

6.3.2 Descriptive analyses

Commercially Confidential Information

7 Statistical methods for safety and tolerability data

All patients within the safety analysis set will be included in the safety data analysis.

Commercially Confidential Information

7.1 Variables

Adverse events, vital signs (blood pressure, pulse rate, body temperature), ECG intervals, laboratory measurements, as well as patient demographics, baseline characteristics, and treatment information.

7.1.1 Variables for gender split analysis

Variables to be used in the gender split analysis for safety and tolerability are: adverse events, vital signs (blood pressure, pulse rate, body temperature), ECG intervals, laboratory measurements.

7.2 Descriptive analyses

Patient demographics and other baseline characteristics

All data for background and demographic variables will be listed by treatment and patient. Summary statistics will be provided by age group and treatment and will also include PIK3CD mutation. Demographic summary will be provided by using the Safety set and all enrolled patients.

Relevant medical history, current medical conditions, results of laboratory screens, drug tests and any other relevant information will be listed by age group, treatment and patient.

Treatment

Data for study drug administration (rescue medication) and concomitant therapies will be listed by age group, treatment and patient.

Vital signs

All vital signs data will be listed by age group, treatment, patient and visit/time, and if ranges are available abnormalities (and relevant orthostatic changes) will be flagged. Summary statistics will be provided by age group, treatment group and visit/time.

Summary statistics will also be provided by gender, treatment group and visit/time.

ECG evaluations

All ECG data will be listed by age group, treatment, patient and visit/time, abnormalities will be flagged. Summary statistics will be provided by age group, treatment group and visit/time.

Summary statistics will also be provided by gender, treatment group and visit/time.

Clinical laboratory evaluations

All laboratory data will be listed by age group, treatment, patient, and visit/time, and if normal ranges are available abnormalities will be flagged. Summary statistics will be provided by age group, treatment group and visit/time.

Summary statistics will also be provided by gender, treatment group and visit/time.

Adverse events

All information obtained on adverse events will be displayed by age group, treatment and patient. The number and percentage of patients with adverse events will be tabulated by body system and preferred term with a breakdown by age group and treatment. A patient with multiple adverse events within a body system is only counted once towards the total of this body system.

All information obtained on adverse events will also be displayed by gender, treatment and patient.

For the legal requirements of ClinicalTrials.gov and EudraCT, two required tables on treatment emergent adverse events which are not serious adverse events with an incidence greater than 0% and on treatment emergent serious adverse events and SAE suspected to be related to study treatment will be provided by system organ class and preferred term on the safety set population.

If for a same patient, several consecutive AEs (irrespective of study treatment causality, seriousness and severity) occurred with the same SOC and PT:

- a single occurrence will be counted if there is ≤ 1 day gap between the end date of the preceding AE and the start date of the consecutive AE
- more than one occurrence will be counted if there is > 1 day gap between the end date of the preceding AE and the start date of the consecutive AE.

For occurrence, the presence of at least one SAE / SAE suspected to be related to study treatment / non SAE has to be checked in a block e.g., among AE's in a ≤ 1 day gap block, if at least one SAE is occurring, then one occurrence is calculated for that SAE.

The number of deaths resulting from SAEs suspected to be related to study treatment and SAEs irrespective of study treatment relationship will be provided by SOC and PT.

Commercially Confidential Information

Pregnancy test

All pregnancy test results for pre-menopausal women who are not surgically sterile will be listed by age group, treatment, patient and visit/time.

Commercially Confidential Information

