CT or MRI imaging in Part I allowed assessment of feasibility with these imaging modalities in APDS/PASLI patients and a first estimation of the effect size.

Part II aims to demonstrate evidence of efficacy and further information on safety and tolerability. Lymphoproliferation, including lymphadenopathy, hepatomegaly, splenomegaly and lymphocytic aggregates in intestinal and bronchial mucosa, is a hallmark of the disease and considered responsible for sequelae such as infections (such as pneumonia), bronchiectasis and obstructions. The second major phenotype of patients with APDS/PASLI is an immunodeficiency leading to frequent bacterial, fungal and viral infections, including opportunistic infections; these infections further contribute to the tissue destruction in the pulmonary tract. Thus, measures for lymphoproliferation and immunodeficiency have been selected as co-primary endpoints in Part II.

Commercially Confidential Information

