5.2.1 Drugs that are prohibited

Other investigational therapies

Other investigational therapies must not be used while the patient is on the study. If such agents are required for a patient then the patient must be permanently discontinued from the treatment portion of the study.

Vaccination

Live/Attenuated Vaccination: The study drug is considered to decrease activities of cells of the immune system, thus from 6 weeks prior to start of treatment, until 7 days after end of study treatment, live vaccines (incl. attenuated viruses) are not permitted.

Dead vaccines: Due to the decreased activities of the immune cells, use of dead vaccines is expected to be less effective or ineffective. Patients should be advised that their vaccination may be ineffective if administered within the timeframe specified above. However, patients will not be discouraged from receiving dead vaccines, including the seasonal influenza vaccination.

Patients and physicians are encouraged to plan required vaccinations outside this window.

Commercially Confidential Information

Commercially Confidential Information

Commercially Confidential Information

Commercially Confidential Information

6 Treatment

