9.1 Adverse events

An adverse event (AE) is any untoward medical occurrence (i.e. any unfavorable and unintended sign [including abnormal laboratory findings], symptom or disease) in a subject or clinical investigation subject after providing written informed consent for participation in the study. Therefore, an AE may or may not be temporally or causally associated with the use of a medicinal (investigational) product.

The occurrence of adverse events should be sought by non-directive questioning of the patient at each visit during the study. Adverse events also may be detected when they are volunteered by the patient during or between visits or through physical examination, laboratory test, or other assessments.

Abnormal laboratory values or test results constitute adverse events only if they fulfill at least one of the following criteria:

- they induce clinical signs or symptoms,
- they are considered clinically significant,
- they require therapy.

Clinically significant abnormal laboratory values or test results should be identified through a review of values outside of normal ranges/clinically notable ranges, significant changes from baseline or the previous visit, or values which are considered to be non-typical in patients with underlying disease. Investigators have the responsibility for managing the safety of individual patients and identifying adverse events. Alert ranges for liver related events are included in [Section 9.4](#).

Adverse events must be recorded on the Adverse Events CRF for patients that pass screening and enter into the study. The adverse events should be reported according to the signs, symptoms or diagnosis associated with them, and accompanied by the following information:

1. the Common Toxicity Criteria (CTC) AE grade (current)

If CTC-AE grading does not exist for an adverse event, use:

- 1=mild,
- 2=moderate,
- 3=severe
- 4=life threatening.

CTC-AE grade 5 (death) is not used, but is collected in other CRFs (e.g. Study Completion, Death/Survival).

2. its relationship to the study treatment (no/yes)
3. its duration (start and end dates) or if the event is ongoing an outcome of not recovered/not resolved should be reported.
4. whether it constitutes a serious adverse event (SAE) See [Section 9.2](#) for definition of SAE
5. action taken regarding [study/investigational] treatment(select as appropriate).

All adverse events should be treated appropriately. Treatment may include one or more of the following:

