9.3 Infection Monitoring

All infections that develop during the study will be reported as AEs. Investigators are requested to specifically enquire about signs and symptoms of infections at each visit, in particular bacterial enterocolitis. Treatment and additional evaluations will be performed at the discretion of the Investigator. WBC count (including differential count) is assessed at every visit. If the neutrophil count falls below 1000 per μ L, then weekly assessments of WBC are recommended until recovery to within 80% of baseline.

The Investigator should consider early treatment with specific antimicrobial therapy on the basis of clinical diagnosis or suspicion thereof, in consultation with infectious disease experts, as appropriate.

The Investigator should remind the patient of the risk of infections and to instruct them to promptly report any symptoms of infections to the Investigator. The patients must also be reminded to always carry their Patient Information Card (with site contact information and which identifies them as participants in a clinical study with an agent with potential immunosuppressive effects) and to show this to any local healthcare provider they may consult and ask that the Investigator be contacted.

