11.5.2 Safety

Vital signs

In Part II, all vital signs data will be listed by treatment, patient and visit/time, and if ranges are available abnormalities (and relevant orthostatic changes) will be flagged. Summary statistics will be provided by treatment group and visit/time.

ECG evaluations

In Part II, all ECG data will be listed by treatment, patient and visit/time, abnormalities will be flagged. Summary statistics will be provided by visit/time.

Clinical laboratory evaluations

In Part II, all laboratory data will be listed by treatment, patient and visit/time, and if normal ranges are available abnormalities will be flagged. Summary statistics will be provided by treatment and visit/time.

Adverse events

In Part II, all information obtained on adverse events will be displayed by treatment and patient. The number and percentage of patients with adverse events will be tabulated by body system and preferred term with a breakdown by treatment. A subject with multiple adverse events within a body system is only counted once towards the total of this body system.

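### The readable Part II adverse event summaries compare neither infection grade nor infection episode rate between arms, although the protocol treats infection as a risk of the drug

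*SAP*

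**What the plan says.** SAP (Part II) 7.2 sets out the main table: "The number and percentage of patients with adverse events will be tabulated by body system and preferred term", broken down by age group and treatment. The counting rule follows: "A patient with multiple adverse events within a body system is only counted once towards the total of this body system". Protocol 11.5.2 has the same rule. No readable Part II table uses severity grade, although Protocol 9.1 has a CTC-AE grade recorded for each event.

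SAP 7.2 has two further outputs:

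- **Listings.** "All information obtained on adverse events will be displayed by age group, treatment and patient".
- **Registry tables.** Non-serious events and serious events are tabulated separately by system organ class and preferred term. Repeat events with the same class and term count as separate occurrences when more than one day lies between them.

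On infection itself, Protocol 5.2.1 says "The study drug is considered to decrease activities of cells of the immune system". Protocol 9.3 makes every infection a reportable adverse event, describes the drug as potentially immunosuppressive, and adds: "Investigators are requested to specifically enquire about signs and symptoms of infections at each visit, in particular bacterial enterocolitis". The design rationale in Protocol 3.1.2 describes the disease as an "immunodeficiency leading to frequent bacterial, fungal and viral infections, including opportunistic infections".

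**The concern.** Safety and tolerability is a Part II objective, and sites are told to probe for infection at every visit. The main by-arm summary nevertheless reduces each patient's infections to yes or no in the body-system total, at any grade. Two kinds of change can then be missed. If infections become more severe without becoming serious, the count does not move. If they become more frequent in a population where most patients already have one, the body-system percentage has little room to rise. A benefit, meaning fewer or milder infections in an immunodeficiency, would be blurred in the same way.

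**Working it through.** **Inputs.** From the documents: 20 active and 10 placebo patients (Protocol 11.6) and 12 weeks of treatment (Protocol 6.2). The documents state no infection or adverse event rate, so the plan has no figure of its own to reproduce here. Assumptions: λ placebo episodes per patient over 12 weeks, with λ from 0.5 to 3, and a true doubling to 2λ on CDZ173.

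**Step 1, grade.** If the same patients have the same infections at a higher grade, every any-grade patient count changes by exactly 0. This needs no rate assumption. If the worse events also become serious, they move into the serious registry table and are visible there. A shift among non-serious events appears in no readable by-arm table.

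**Step 2, frequency.** With Poisson counts, the share of patients with at least one infection is 1 − exp(−λ) on placebo and 1 − exp(−2λ) on CDZ173. For λ = 2: 1 − exp(−2) = 86.5% and 1 − exp(−4) = 98.2%.

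The next table adds the exact binomial chance that the observed active percentage is no higher than placebo. It also gives two yardsticks of information, since the plan tests neither: two-sided 5% power of Fisher's test on patients, and of the conditional binomial test on episodes.

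| λ | Placebo | CDZ173 | Gap (points) | Chance active % ≤ placebo % | Fisher, patients | Episode counts |
|---|---|---|---|---|---|---|
| 0.5 | 39.3% | 63.2% | 23.9 | 13% | 16% | 25% |
| 1 | 63.2% | 86.5% | 23.3 | 11% | 26% | 50% |
| 2 | 86.5% | 98.2% | 11.7 | 25% | 11% | 83% |
| 3 | 95.0% | 99.8% | 4.7 | 60% | 1% | 95% |

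At λ = 3 the expected episodes are 10 × 3 = 30 on placebo and 20 × 6 = 120 on CDZ173, yet the expected percentages differ by under 5 points.

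**Step 3, variation between patients.** With negative binomial counts of dispersion k, the share is 1 − (1 + kλ)^(−1/k). Episode counts are here compared by Mann-Whitney in 4,000 simulated trials.

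| k | λ | Placebo | CDZ173 | Fisher, patients | Episode counts |
|---|---|---|---|---|---|
| 0.5 | 1 | 55.6% | 75.0% | 16% | 28% |
| 0.5 | 2 | 75.0% | 88.9% | 13% | 37% |
| 0.5 | 3 | 84.0% | 93.8% | 8% | 43% |
| 1 | 3 | 75.0% | 85.7% | 8% | 24% |

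Overdispersion makes the total saturate less and reduces what counts add, but they still add something.

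**Step 4, precision of a rate ratio.** The standard error of the log rate ratio is about √(1/(10λ) + 1/(40λ) + k(1/10 + 1/20)). For λ = 2 and k = 0.5 this is √(0.05 + 0.0125 + 0.075) = 0.371. An estimated ratio of 2 would then have a 95% interval of about 2 × exp(±1.96 × 0.371), or 0.97 to 4.14.

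**The case against.** The strongest case against is that the plan already shows much of this.

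- **Preferred-term rows** saturate less than the body-system total. If 3 placebo episodes were spread evenly over five terms, each row would read 1 − exp(−0.6) = 45% against 1 − exp(−1.2) = 70%. This stands, but a signal spread over many sparse rows and two age groups is harder to read than one total.
- **The registry tables** count repeat occurrences and separate serious events. This also stands. They are split by seriousness, merge records only within one term, and carry neither grade nor patient-time. The text does not state a treatment breakdown for them.
- **Listings** hold every event for about 30 patients, but they are not a comparison.
- **Oversight during the trial** includes a DMC seeing unblinded data (Protocol 6.5, 10.3) and a hold rule using related Grade 3 or higher events (Protocol 7.4). Neither defines the reported comparison.
- **A fixed 12-week period** makes patient-time matter less. That is true unless stopping differs by arm. Protocol 7.1 requires treatment to stop for some gastrointestinal infections, so time on treatment may depend on the outcome being counted.

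A reader might infer that nearly all these patients will have an infection on study, so that the plan would hide a doubling. The documents do not support that. They call infections frequent, give infection history only as an example joined by and/or in inclusion criterion 3, and state no 12-week incidence. At one placebo episode the 23-point gap would be plain.

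A reader might also infer that no severity or infection output exists. Redacted blocks sit in SAP section 7, including directly after the adverse event text, so absence cannot be asserted. Nor is infection the only monitored risk: liver and renal safety have their own sections (Protocol 9.4, 9.5).

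**Conclusion.** The point holds in a limited form. In the readable text, a change in CTC-AE grade among non-serious infections is invisible in every by-arm summary, whatever the infection rate. Insensitivity of the body-system total to frequency is conditional. Under an assumed doubling with Poisson counts it is strong at about 2 to 3 placebo episodes per patient over 12 weeks and weak at 1 or fewer, and it is milder with overdispersion. No readable output gives, by arm, a single infection episode total, a grade summary or a rate per patient-time. It does not follow that the safety objective would be answered wrongly. The plan leaves a gap in how an infection signal is summarised, and the gap is cheap to close.

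**What to change.** First confirm whether a redacted output or table shell already covers this. If not, add one descriptive by-arm table to SAP (Part II) 7.2, all ages together, with separate rows for the infections body system and for one pre-listed grouping of enterocolitis and diarrhoea terms. It should show:

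- (a) patients by worst CTC-AE grade, including grade 3 or higher;
- (b) number of episodes and episodes per patient-time on treatment, with a rate ratio and 95% confidence interval from a model that allows for overdispersion. Events and time should cover the same period.

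Define an episode at the level of the grouping: overlapping or adjacent records (gap of 1 day or less) count once even when coded to different preferred terms. The existing one-day rule works only within a single term, so one illness coded under two terms would otherwise count twice. Keep the planned tables.

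The cost is SAP wording and one table. Start and end dates, grade and MedDRA-coded terms are already collected (Protocol 9.1, 10.2). With 30 patients the interval will be wide, so the result should be labelled descriptive.
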